Population:	 Approximately 300 male and female participants in the US, 18 years of age or older, irrespective of left ventricular ejection fraction with symptomatic HF will be enrolled. Patients must be able to stand independently on the Bodyport Cardiac Scale. We will exclude patients with a weight > 170 kg, prior heart transplant or currently listed for heart transplant, current LVAD, current inotropes, and end-stage renal disease requiring chronic dialysis.
Sites Enrolling	Approximately 5 US sites
Participants:	
Duration of Study	Approximately 1 year (6 months enrollment and approximately 6 months follow up)
Study Product	Bodyport Cardiac Scale

Figure 1. SCALE-HF Overall Design. Scale-HF 1 will be the first in a series of studies that aims to evaluate the use of the Bodyport Cardiac Scale to rapidly identify early worsening HF in order to allow for clinical interventions to prevent disease progression.

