4.1 OVERALL STUDY DESIGN

SCALE-HF 1 is a prospective, multicenter study. The overarching goal is to enroll a broad population of patients with HF and follow them remotely for clinical events. Patients will be identified by participating sites and may be consented and enrolled remotely, in clinic, or prior to hospital discharge. Follow-up visits will be remote and occur at 6 weeks, 3 months and then every 3 months until the end of the study. Follow-up information will be collected by sites and may be supplemented by a centralized telephone call center (and email) via trained personnel at the Duke Clinical Research Institute. Participants may also be contacted by the site and/or study team at other timepoints for study issues such as suspected device malfunction or nonadherence with the Bodyport Cardiac Scale.

Patients eligible for the study will have HF and a prior history of hospitalization for acute decompensated HF. A history of clinical HF will be confirmed by site investigators. To ensure that a broad population of patients is enrolled, there will be limited additional inclusion and exclusion criteria. The participant population is described in more detail in Section 5 below.

All patients will consent for longitudinal follow-up. This will include remote follow-up visits as well as access to clinical records to evaluate for future clinical events. The remote follow-up visits will place a minimal burden on patients and sites and be limited to assessments for suspected clinical events. All patients will consent to release of medical records regarding HF history and suspected clinical events. Based on site- and participant-reported events, medical records for possible clinical events will be collected. Possible clinical events will be reviewed and adjudicated by a clinical events committee using standardized definitions. The committee members will be blinded to sensor and algorithm data.

Training on device use will be provided to patients and daily utilization of the Bodyport Cardiac Scale will be requested. Device sensor data will be uploaded remotely and analyzed on an ongoing basis throughout the study. Patients, study teams, and treating clinicians will be blinded to the investigational sensor data other than basic information that is currently available through other devices including weight, heart rate and leg edema status. There will be no attempt to utilize the study data to influence clinical practice.

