4.2 SCHEDULE OF EVENTS

	Baseline Visit	Follow-up Visits
Eligibility criteria	Х	
Informed consent	Х	
Demographics ^a	X	
Laboratory evaluations ^b	Х	
Electrocardiogram	X	

Table 2. SCALE-HF 1 Schedule of Events

Relevant medical history ^c	Х	
Implantable device data ^d		Х
HF outcomes ^e		Х
Arrhythmic events requiring hospitalizations ^f		Х

^a Includes date of birth, sex, race, ethnicity

^b Includes most recent basic metabolic panel (sodium, potassium, blood urea nitrogen, serum creatinine) and natriuretic peptide levels, B-type natriuretic peptide (BNP) or N-terminal pro-BNP. Where available will collect right heart cath data. ^c Includes heart failure history including last assessment of left ventricular ejection fraction

^d Patients with cardiac implantable electronic devices including pulmonary artery sensors and implantable cardioverter defibrillators will provide routine interrogation data

^e Hospital readmissions and all-cause mortality.

^fHospitalization event or treatment for ventricular arrhythmia (shock by defibrillator)

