6.2 SURVEILLANCE/FOLLOW UP

Follow-up will occur remotely at 6 weeks, 3 months and then every 3 months until the end of the study. Follow-up will occur via telephone interviews by trained personnel by individual participating sites. This approach will ensure the consistency and quality of data collection and minimize loss to follow-up. At each interview, participants will be asked to report any encountered clinical events.

Routine data collection at each follow up timepoint will include:

• Possible clinical event including those that occur outside of the enrolling health system such as hospitalization, emergency room visit or clinic visit with IV diuretic administration

Based on participant-reported events, clinical data for rehospitalizations, emergency department visits, and worsening heart failure related clinic visits will be obtained and submitted for review. As an additional mechanism to safeguard against under-reporting of events, sites will conduct medical record queries at 6 weeks, 3 months and then every 3 months until the end of the study enrollment to screen for hospitalizations or procedures.

Patients may also be contacted by the site and/or study team including the sponsor and coordinating center for suspected device malfunction or nonadherence with the Bodyport Cardiac Scale. Nonadherence is defined as device non-use for 3 days or more. Patients will be potentially contacted using email, phone calls or text messaging to provide reminders to use the scale. Should non-use continue beyond 4 days the patient may be contacted by a phone call to explore potential problems with the technology or explore whether an event might have occurred.

Upon study discontinuation the patients are asked to return the scale to the company and are provided with a return shipping label.

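### No event check is fixed at the end of a participant's scale use, so up to just under 3 months of scale data may have no scheduled event ascertainment

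*Protocol*

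**What the plan says.** Interviews: section 6.2 states "Follow-up will occur remotely at 6 weeks, 3 months and then every 3 months until the end of the study", and section 4.1 gives the same grid. The event check is made at these contacts: "At each interview, participants will be asked to report any encountered clinical events".

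Record queries: section 6.2 adds site record queries as a safeguard against under-reporting. They start on the same grid but have a different end point: "3 months and then every 3 months until the end of the study enrollment to screen for hospitalizations or procedures".

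Scale data: section 4.1 states "Device sensor data will be uploaded remotely and analyzed on an ongoing basis throughout the study", so collection is not tied to the last event check.

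End of participation: section 6.2 states "Upon study discontinuation the patients are asked to return the scale to the company and are provided with a return shipping label". Sections 12.2 and 13 allow withdrawal by the participant and discontinuation by a site or the sponsor at any time. Neither asks for a final event check. Table 2 in section 4.2 has one baseline column and one follow-up column.

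Duration: the Protocol Summary gives "Approximately 1 year (6 months enrollment and approximately 6 months follow up". It does not say whether each participant has a fixed 6 months or whether all stay until a common closing date.

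**The concern.** Contacts count from each participant's own enrolment, whereas the grid runs to the end of the study. Unless a participant's last scale day coincides with a contact, the days after the last contact have sensor data but no scheduled question about events. A participant followed for 8 months, for example, is interviewed at month 6 and would next be due at month 9, after closure.

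Section 10.1 says models will be evaluated and optimised on sensitivity and specificity for heart failure events, so both measures depend on complete event capture. The error runs one way, because events can be missed but not added. A missed event removes a possible true positive. If the days around it are kept, a correct alert before it looks false. An analysis plan could exclude unchecked days, but it could not recover events that nobody sought.

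**Working it through.** **Inputs from the protocol.** About 300 participants, about 75 primary endpoints, 25% at 6 months (section 10.3). Enrolment of 6 months and approximately 6 months of follow-up (Protocol Summary). Contacts at 6 weeks, 3 months and every 3 months after that (sections 4.1 and 6.2).

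**Assumptions not in the protocol.** Uniform enrolment, a common closing date at month 12, and a constant hazard.

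**The plan's own figure.** 300 × 0.25 = 75, which reproduces.

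**Gap under common closure.** Time on study T is uniform on 6 to 12 months. The last contact is L = 3 × floor(T/3), so L = 6 for T below 9 and L = 9 from there to 12. The gap is T − L.
- Range: 0 to just under 3 months. Mean: 1.5 months.
- Share of follow-up: mean T = 9 months, and 1.5 / 9 = 16.7%.
- Two thirds of participants have a gap over 1 month.

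**First events in the gap.** Hazard h = −ln(0.75) / 6 = 0.0479 per month. Survival to 6, 9 and 12 months is 0.7500, 0.6495 and 0.5625.
- For T in 6 to 9: mean survival at T is (0.7500 − 0.6495) / (3h) = 0.6986, so the gap probability is 0.7500 − 0.6986 = 0.0514.
- For T in 9 to 12: mean survival at T is (0.6495 − 0.5625) / (3h) = 0.6050, so the gap probability is 0.6495 − 0.6050 = 0.0446 (unrounded inputs).
- First events in the gap: 300 × (0.0514 + 0.0446) / 2 = 14.4.
- All first events: 300 × [1 − (0.6986 + 0.6050) / 2] = 104.5.
- If recurrences count at the same constant rate: 300 × h × 1.5 = 21.6 in the gap, out of 300 × h × 9 = 129.5.

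**Sensitivity to minimum follow-up.** With 5 to 7 months in place of 6, the mean gap stays at 1.5 months, the share runs from 19% to 15%, and first events in the gap run from 16 to 14.

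**Alternative reading: fixed follow-up per participant.**

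| Fixed follow-up (months) | Gap (months) |
|---|---|
| 5.5 | 2.5 |
| 6.0 | 0 |
| 6.5 | 0.5 |
| 7.0 | 1.0 |

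Under either reading, a participant who leaves between contacts has a gap.

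**Record queries read literally.** If they stop when enrolment closes at month 6, half of participants (enrolled at least 3 months by then) are covered to month 3, a quarter to 6 weeks, and a quarter have none. Mean coverage is 0.5 × 3 + 0.25 × 1.5 = 1.9 months. If the phrase means the individual's own participation, the queries follow the interview grid and leave the same gap.

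**The case against.** The strongest objection is that about 6 months per participant fits the protocol's figures at least as well. The Protocol Summary allows that reading, and section 10.3 reaches 75 events from 25% at 6 months, whereas common closure at month 12 implies about 104 first events. With exactly 6 months each, the 6-month interview is the close-out and completers have no gap. This stands as a limit on the size. It does not remove the point, because the protocol does not settle the question, the open-ended grid also fits variable follow-up, and early leavers are exposed either way. The wording of the grid could also be taken to imply a contact at study end, but none is scheduled.

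Other routes could catch late events. Sites may be queried, the coordinating center's call center may supplement follow-up, and non-use beyond 4 days may prompt a call. All are optional. An emergency visit, or a clinic visit for IV diuretics, need not interrupt scale use for that long. These routes would reduce the loss but do not reliably close the gap.

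The scale-return sentence is device logistics and is not wrong in itself, and Table 2 collapses all follow-up contacts into one column, so neither is strong evidence alone. The firmer textual defect is that record queries and interviews have different end points.

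A reader might infer that the unchecked days will enter model development as event-free time. The protocol does not say so. Rules for labelling or censoring sensor days may sit in an analysis plan that is not shown, and their absence here is not a finding.

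**Conclusion.** The point holds for ascertainment: the protocol fixes no event check at the end of scale use, and its back-up record queries are worded to stop at the end of enrollment. For participants who stay to a common closing date or leave between contacts, the gap is up to just under 3 months. Under uniform enrolment, month-12 closure and constant hazard it averages 1.5 months, about 17% of follow-up, and contains about 14 of 104 first events. It is near zero for completers if every participant stops at the 6-month contact.

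The 14 should not be read as the number of events lost. It counts first events at risk of being missed, with no allowance for site reports or non-use calls. Events that are missed would bias the sensitivity and specificity on which the model is optimised. How strongly depends on how unchecked days are handled, which this document does not state. The protocol should be changed, because contact timing is set there and the remedy is cheap.

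**What to change.** - Add to section 6.2 and Table 2 a closing event interview and medical record query for every participant at study end or withdrawal, timed with the scale return.
- Change the end point of the record queries from the end of enrollment to the end of each participant's follow-up.
- Where no closing check is completed, end that participant's analysable scale data at the last completed event check.

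The cost is one call and one chart query per participant, plus some sensor days lost for those who cannot be reached. The call can be made when the return of the scale is arranged.

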7. COMPENSATION

Participants will not receive any compensation for participating in this study.

8. COSTS

Participants will not incur any additional costs due to study participation. Patients or their insurance company will be required to pay for all expenses related to regular care such as outpatient visits and other hospital care.

9. SAFETY MONITORING

No safety related concerns are expected with the non-invasive scale. No safety specific / adverse endpoints are defined

10. STATISTICAL METHODS AND DATA ANALYSIS

10.1 STATISTICAL AND ANALYTICAL PLANS

The Bodyport Cardiac Scale captures various physiological signals including an electrocardiograph, an impedance plethysmograph, and a ballistocardiograph. These raw signals will be filtered and interpolated prior to feature extraction and model validation. Regions with motion artifacts or noise will be identified and removed. Ensemble average waveforms will be constructed from the real-time signals. Specific characteristic features will be identified on the averaged waveforms. Temporal and amplitude-based biomarkers will be extracted from the identified features within and across each averaged waveform. These features and biomarkers will be assessed longitudinally by constructing trends consisting of multiple measurements and identifying statistically significant changes over time. Some of the key features being explored in this study are: weight, heart rate, heart rate variability, peripheral impedance, body fluid, balance, stroke volume, cardiac output, pre-ejection period, left ventricular ejection time, as well as the amplitude and timing of characteristic features on the IPG, ECG, and BCG signals. A focus on these specific features is driven by prior research demonstrating clinical relevance to cardiovascular function and heart failure status.

During analysis, various methods will be implemented to select signal features that demonstrate a meaningful association with HFEs. Those features most strongly correlated to HFEs will be combined into a model and associated alert algorithm. The development of the model may use a combination of techniques, including multivariate regression and machine learning (e.g. support vector machines, clustering, decision trees, Bayesian networks). Models will be evaluated and optimized based on their sensitivity and specificity to detect heart failure events.

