10.2 INTERIM ANALYSIS

Throughout the study, enrollment rates, heart failure event prevalence, and adherence will be analyzed.

Additionally, at 100 enrolled patients with approximately 90 day follow up, an interim analysis may be performed. Data will be shared with Bodyport for statistical analysis and possible publication. Bodyport will use the scale biomarker data to validate a model that reflects changes in patient status. The model will use intra-patient biomarker trends to detect meaningful deviations from a patient's baseline state.

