10.3 SAMPLE SIZE

Data derived from this study will add to the model development aims of the Bodyport Cardiac Scale. This study is statistically powered to detect approximately 75 primary endpoints which will approximate to about 300 enrolled patients. An event rate of 75 equates to an approximate rate of 25% at 6 months. Given that this study is a development study however additional events may be required to derive the predictive algorithm.

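### Does Section 10.1 build in an overstated sensitivity by selecting features on their correlation with events and then scoring the models in one cohort?

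*Protocol*

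**What the plan says.** Section 10.1 sets out how the algorithm will be built. First, "various methods will be implemented to select signal features that demonstrate a meaningful association with HFEs". Next, "Those features most strongly correlated to HFEs will be combined into a model and associated alert algorithm". Finally, "Models will be evaluated and optimized based on their sensitivity and specificity to detect heart failure events". The techniques listed run from regression to several kinds of machine learning. The candidate list has ten named signals plus an uncounted set of waveform amplitudes and timings. The same section mentions model validation as a step after signal processing, without describing it, and says that the choice of signals rests on earlier research.

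The data are repeated within patients. In Section 4.1, "daily utilization of the Bodyport Cardiac Scale will be requested", and Section 10.1 describes "constructing trends consisting of multiple measurements and identifying statistically significant changes over time". Section 10.2 allows an optional interim look, in which "Bodyport will use the scale biomarker data to validate a model that reflects changes in patient status".

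On size, Section 10.3 states: "This study is statistically powered to detect approximately 75 primary endpoints which will approximate to about 300 enrolled patients". It also calls this a development study and allows that more events may be needed to derive the algorithm. The protocol summary places SCALE-HF 1 first in a programme of several phases.

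**The concern.** One pair of measures both tunes and grades the models, features are kept because they correlate with the outcome, and only one cohort is described. Read as a recipe applied once to all 300 patients, this is a well-known route to optimistic accuracy: some features survive by chance, and the data that favoured them then confirm them.

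Two common safeguards would not help if applied carelessly. Cross-validation begun after selection on the full data leaves the selection bias in place. Splitting daily readings at random puts neighbouring, correlated days of one patient in both the fitting and the test part.

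Sensitivity and specificity are the only performance measures named, so an alert algorithm could look better at catching events than it would prove in new patients, and a later phase might be planned on that figure.

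**Working it through.** **The plan's own figure.** 75 / 300 = 0.25, and 0.25 × 300 = 75, so the event count, enrolment and 25% rate at 6 months in Section 10.3 agree. No hypothesis, target sensitivity or error rate is stated, so there is no power calculation to reproduce.

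**Inputs.** From the protocol: 300 patients, 75 events, about 6 months of daily readings, selection by association with events. Assumed, because the protocol does not give them: number of candidate features, number kept, signal strength, autocorrelation, alert window and cut-off rule. The results below are therefore illustrations.

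**Simulation with daily readings.** Settings: 180 days, autocorrelation 0.9, 7-day means taken as deviations from the patient's own baseline, 14-day windows, cut-off by the Youden index, 80 runs per setting. With 16, 32 and 100 independent candidates, 5, 8 and 8 are kept. Three features shift before an event in the signal settings. Entries are sensitivity in the same data minus sensitivity in new patients, in percent.

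| Signal | 16 candidates | 32 candidates | 100 candidates |
|---|---|---|---|
| 1.0 SD | 77.3 − 70.4 = 6.9 | 78.0 − 68.5 = 9.5 | 77.9 − 65.2 = 12.7 |
| 0.6 SD | 68.2 − 58.4 = 9.8 | 70.5 − 54.8 = 15.7 | 70.0 − 50.7 = 19.3 |
| none | 59.6 − 41.0 = 18.6 | 66.6 − 41.8 = 24.8 | 65.8 − 37.4 = 28.4 |

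Specificity is overstated by only 0.4 to 2 points.

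**Separate simulation, one row per patient.** Settings: specificity fixed at 85%, up to 10 features kept, linear discriminant model, three weak true features (0.4 SD each), 300 runs per setting. Entries are sensitivity in percent.

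| Candidates | Same data | Cross-validation after full-data selection | Selection inside patient-level folds | New patients |
|---|---|---|---|---|
| 10 | 41.5 | 31.8 | 31.8 | 33.0 |
| 30 | 46.6 | 37.7 | 29.0 | 29.6 |
| 100 | 51.6 | 43.3 | 25.7 | 27.0 |
| 300 | 57.0 | 49.4 | 23.2 | 24.7 |

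Cross-validation after full-data selection overstates by 8.1 points (37.7 − 29.6) with 30 candidates and by 24.7 points (49.4 − 24.7) with 300. With 10 candidates, all kept, it does not overstate. Selection inside patient-level folds stays within 1.5 points of the truth.

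**Splitting by day.** Settings: pure noise, autocorrelation 0.8, selection inside folds, specificity 85%, so chance sensitivity is 15%. A day split gives 25 to 32% for a linear model and 61 to 65% for nearest neighbours, against 15 to 17% when whole patients are held out. Only six runs per setting were made, so these are rough.

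**Scale.** With 75 events the 95% half-width for a sensitivity of 0.5 is 1.96 × √(0.5 × 0.5 / 75) = 0.113, and for 0.8 it is 1.96 × √(0.8 × 0.2 / 75) = 0.091. The bias could exceed sampling error.

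**The condition.** Every inflated figure above requires that selection used the test patients, that scoring used the fitting data, or that patients were split across folds. Section 10.1 states none of these. Its order of steps is the same in the column that works (selection inside patient-level folds) as in the columns that fail.

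**The case for a change.** The best argument for changing the protocol is that it does fix a selection rule and a scoring rule, and stops just where the safeguard belongs. A general promise to cross-validate would not settle the matter, since two ordinary versions fail. The safeguard would cost two sentences and no patients. Interim and final results may be published, so an inflated figure could travel.

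The arithmetic of this stands. The earlier research behind the signals makes the no-signal row the least relevant, but a gap of about 7 to 13 points remains even with a strong signal. The development label limits the harm without correcting a wrong figure.

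What does not stand is the step from hazard to error. The conditions that produce the bias are supplied by the reader. The added sentences would correct nothing in Section 10.1. They would write down a resampling scheme, and patient-level nested resampling is only one sound choice beside a patient-level hold-out or evaluation in a later phase.

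The interim look adds nothing: it is optional and is described in terms of changes in patient status. Section 10.2 says that "The model will use intra-patient biomarker trends to detect meaningful deviations from a patient's baseline state", which does not make worsening heart failure events the reference.

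**Conclusion.** No change to the protocol follows. The concern describes what would happen if the analysts failed to keep selection, tuning and testing apart: roughly 7 to 19 points of excess sensitivity when a moderate or strong signal exists, more when the signal is weak or absent and the candidates are many, and little effect on specificity. These sizes rest on assumed feature counts, signal strengths and autocorrelation, and on independent features in the tabulated runs.

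The protocol neither states nor implies that failure. It describes the usual sequence of model building, names validation as a step, claims no accuracy and sets no success threshold. Which patients are held out, and at which stage selection is repeated, is a gap that a competent analyst fills and that a statistical analysis plan, not seen here, would normally cover. Anyone reading the eventual sensitivity and specificity should ask whether they come from patients who played no part in selection, tuning or the choice of cut-off. That question is for the analysis plan and the report.
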